### **Data Analysis**

MRI data will be analyzed blindly by one of the investigators ([name]) using a commercial post-processing package (CMR42, Circle Cardiovascular Imaging Inc., Calgary AB). CMR42 function module performs global and regional LV function analyses on slices acquired in short axis orientation. LV volumes and myocardial mass are calculated with trabeculae and papillary muscles included. The CMR42 flow module computes velocity, flow, regurgitant volumes, and cardiac output. Ejection fraction (EF) is computed using end diastolic volumes (EDV) and end systolic volumes (ESV). For determining differences before and after  $\beta$ -OH-B, dimensional parameters are normalized to body surface area (BSA), using Mosteller formula (81). Ejection and filling functions are assessed from the respective maximal and average downslope and upslope of volume time curves to determine peak LV ejection (PLVER) and filling (PLVFR) rates.

PET sinograms are corrected for tissue attenuation and reconstructed through standard reconstruction algorithms. Image manipulation and data handling are performed using Carimas 2 (Turku PET Centre, Turku, Finland) software (82). The input function for FDG is derived from continuous monitoring of arterialized blood radioactivity. Whole blood is converted into plasma input using a limited number of discrete plasma samples. Delay correction is performed. Arterial input for O-water is obtained from the left atrium time activity curve. All of the PET data will be analyzed by [name] who has been a long term collaborator with Diabetes Division faculty members (19,20,22,78,79).

## Statistical Analysis

Data are expressed as mean  $\pm$  SD or as percentages. Statistical analyses will be performed using R 3.2.1 statistical software with RStudio IDE, Version 0.99.467. Paired, two-sided Student's t-test will be used to evaluate the null hypothesis of no difference between baseline and post  $\beta$ -OH-B butyrate protocol.  $p<0.05$  is deemed significant. Pearson's product-moment correlation will be used to examine the relationship between changes in parameters of LV diastolic and systolic function and coronary blood versus changes in myocardial  $\beta$ -OH-B uptake and both univariate and multivariate ANOVA for changes in EF in the 3 different  $\beta$ -OH-B infusion groups.

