**Table 2. Events for subjects in GROUP II:**

Visit Assessments Schedule	Visit 1 Screening DAY -30 to -7	Visit 2 MRI Study 1 Day 0-30	Visit 3 MRI Study 2 Day 7-30 after MRI Study 1	Visit 4 PET Study 1 Day 7-30 after MRI Study 2	Visit 5 PET Study 2 Day 7-30 after PET Study 1
Routine Blood Chemistrys, CBC, UA, lipid profile, TSH/T4, A1c, NT-proBNP, hCG	X				
ECG, DXA, ECHO (if not done within 3-6 months of screening)	X				
POC urine pregnancy test				X	X
Vital signs	X	X	X	X	X
Baseline Cardiac MRI and baseline blood samples $\times$ 3: $\beta$ -OH-butyrate, acetoacetate, glucose, FFA, lactate, pyruvate, glycerol, HCO 3 , insulin/C-pep, glucagon, renin and aldosterone		X	X		
Blood safety monitoring before (3 samples) and after (3 samples) the infusion: glucose, potassium with iSTAT		X	X	X	X
6-hour prime-continuous infusion of $\beta$ -OH-B (0.8 M solution; pH adjusted to 7.24) to increase the plasma $\beta$ -OH-		X		X	
6-hour prime-continuous infusion of NaHCO 3 (0.12 M solution); volume to be infused will be the same as $\beta$ -			X		X
Post-infusion Cardiac MRI and blood samples $\times$ 3: NT-proBNP, $\beta$ -OH-butyrate, acetoacetate, glucose, FFA, lactate, pyruvate, glycerol, HCO 3 , insulin/C-pep,		X	X		

18F-2-DOG/15O-H 2 O PET study and blood samples x 12: NT-proBNP, $\beta$ -OH-butyrate, acetoacetate, glucose, FFA, lactate, pyruvate, glycerol, HCO 3 and hematocrit (with iSTAT), insulin/C-pep and glucagon, erythropoietin, urine 18F-radioactivity.				X	X
---	--	--	--	---	---

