Currently, it is not known what plasma  $\beta$ -OH-B level is required to observe an improvement in LV diastolic/systolic function. Based upon the study of Gormesen et al (70), we anticipate that an increase in plasma  $\beta$ -OH-B of ~2 mmol/L will be adequate to augment myocardial  $\beta$ -OH-B uptake sufficiently to switch the myocardium from glucose to ketone utilization and result in an improvement in cardiac function. Therefore, subjects in GROUP II will be studied on two occasions with NaHCO3 infusion to serve as time controls. Since we previously have shown that Na- The total volume of  $\beta$ -OH-B and NaHCO3 to be infused will be the same to obviate any effect of volume on cardiac function. Blood glucose and electrolytes will be monitored similarly as described above for  $\beta$ -OH-B infusion. As mentioned above, the volume will not exceed 300 ml to avoid volume overload. We are unaware of any evidence that the NaHCO3 infusion has any effect on cardiac function. We have not included a time control study for the low and high dose B-OH-B infusion studies although, depending

upon the results with the lower and higher B-OH-B infusions, we may choose to perform the control NaHCO3 infusion in these groups as well.

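### Group II's NaHCO3 control sessions appear in no stated analysis, so the before-after test credits any systematic time, infusion or repeat-scan change to ketones

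*Combined protocol and SAP*

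**What the plan says.** **Design.** The Study Protocol text states that "subjects in GROUP II will be studied on two occasions with NaHCO 3 infusion to serve as time controls". It adds that the volumes of the two solutions "to be infused will be the same to obviate any effect of volume on cardiac function". Table 2 gives NaHCO3 its own MRI visit, with scans before and after infusion, and its own PET visit. The row reads "6-hour prime-continuous infusion of NaHCO 3 (0.12 M solution); volume to be infused will be the same as" that of β-OH-B. For the other two groups the text says "We have not included a time control study for the low and high dose B-OH-B infusion studies", and leaves open adding one later depending on results.

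**Analysis.** Statistical Analysis lists three items:

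- a "Paired, two-sided Student's t-test will be used to evaluate the null hypothesis of no difference between baseline and post" β-OH-B;
- Pearson correlations between changes;
- "univariate and multivariate ANOVA for changes in EF in the 3 different" infusion groups.

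In Data Analysis, the sentence on normalising cardiac dimensions is likewise framed as "For determining differences before and after" β-OH-B. Neither section mentions NaHCO3 or a contrast between sessions.

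**PET.** 15O-water blood flow is measured before the infusion and again during it. FDG is injected once per session, at 300 minutes. The comparator is a separate NaHCO3 session, with the order of the two PET studies randomised.

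**The concern.** A before-after difference on the β-OH-B day contains the ketone effect plus anything else that moves systematically over the session: hours of fasting and lying still, the infused fluid, and a second scan. The sponsor added the NaHCO3 day to separate these, but the stated test looks at the β-OH-B day alone.

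Expected Results would read a significant improvement in LV function as support for the ketone hypothesis. Under the written plan, a significant Group II change could be drift, although the data that could show this are already being collected. Because the controlled contrast is not named, the choice between a before-after result and a controlled one is left until the data are seen.

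**Working it through.** **Inputs.** Sample Size gives a baseline EF of 45 ± 2%, an autocorrelation of 0.96, alpha 0.05, 90% power and 23 subjects per group before dropout. The procedures text has 19 per group. Infusion rates, the 100 mg/mL concentration and scan times come from Study Protocol. Drift size and the correlation r between the two sessions' changes are assumptions, because the documents give neither.

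**1. The plan's own figure.** SD of change = 2 × √(2 × (1 − 0.96)) = 0.566 EF points. With a 10% relative increase (0.10 × 45 = 4.5 points) and a two-sided paired t-test, 90% power needs about 3 subjects, not 23. The 23 comes back only for a change of about 0.40 points. That mismatch is a separate problem; the present point does not depend on it.

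**2. Before-after test under pure drift.** No ketone effect, noncentral t, noncentrality = drift × √n / 0.566:

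| Assumed drift (EF points) | False significance, n = 23 | n = 19 |
|---|---|---|
| 0.2 | 37% | 31% |
| 0.3 | 68% | 59% |
| 0.4 | 90% | 83% |

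Nominal rate: 5%. The controlled contrast is (post − pre on the β-OH-B day) − (post − pre on the NaHCO3 day). Drift common to both days subtracts out, and its error rate stayed at about 5% in simulation.

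**3. Hypothetical larger SDs.** Solving backwards from n = 23 gives an SD of change of 6.36 for a 4.5-point target, or 14.1 for a 10-point target. Drifts of 1, 2 and 3 points then give 11%, 30% and 58%, or 6%, 10% and 16%. The stated inputs cannot produce these SDs: with SD 2 at both scans, the SD of change is at most 2 × √(2 × (1 + 1)) = 4. They are illustrations only.

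**4. Does the ANOVA fill the gap?** Partly. Drift common to all groups cancels between groups, and Groups I and II share the 6-hour schedule and repeat-scan time. But the ANOVA covers EF only, has no zero-ketone group and includes a 3-hour group, and no random allocation to dose groups is stated. Planned volume also rises with dose. At the start of the repeat MRI (5, 5 and 2 hours):

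- Group I: (0.4 × 20 + 0.2 × 280)/100 = 0.64 mL/kg
- Group II: (1.5 × 20 + 0.75 × 280)/100 = 2.40 mL/kg
- Group III: (4.0 × 20 + 2.0 × 100)/100 = 2.80 mL/kg

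These are before the stated cap ("the volume will not exceed 300 ml to avoid volume overload").

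**5. FDG.** With one injection per session, during the infusion, there is no pre-infusion FDG value. The worded baseline-versus-post test therefore does not fit this endpoint.

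**6. Cost in precision.** SD of the contrast = 0.566 × √(2 × (1 − r)), which is 0.80 at r = 0 and 0.566 at r = 0.5. The 90%-power detectable effect at n = 23 is 0.7075 × SD: 0.40 points before-after, 0.57 for the contrast at r = 0, and 0.40 again at r = 0.5.

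**The case against.** The strongest reply is that the sponsor plainly means to use the control: the text states its purpose and matches its volume. That is fair, and a reader should not infer an uncontrolled Group II design or an intention to discard the sessions. The gap is in the analysis sections, which name neither the contrast nor its priority.

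Other points stand in part:

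- **Drift is assumed.** Nothing in the documents shows that EF drifts. The plan cites the reproducibility of cardiac MRI and has the images analysed blindly. Random scan error is already in the SD of change; only a systematic shift biases the test. Blinded analysis and good reproducibility do not remove a real change over hours of infusion.
- **The ANOVA offers some protection.** It would be wrong to call it useless, and common drift alone would not produce the expected dose-response. Its limits remain those in the working.
- **The missing controls in Groups I and III are disclosed,** with the option of adding them. That is openness about a limitation, but it does not make those before-after results controlled.
- **MRI order.** A reader might infer from Table 2, which lists β-OH-B first, that the MRI order is fixed. The table lists PET the same way, and PET order is randomised, so column order proves nothing. The MRI order is simply not clear.
- **FDG.** A reader might infer that the glucose-uptake aim cannot be analysed. It can: the design leaves one obvious comparison between sessions, so this is mainly a wording gap.

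**Conclusion.** The concern holds for Group II's EF, other MRI endpoints and 15O-water blood flow: the stated test cannot separate ketones from a systematic session effect, and no listed analysis uses the sessions scheduled to do so. This must be fixed, because it decides whether the main mechanistic claim rests on controlled evidence.

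The size depends on drift that the documents do not quantify. On the stated SD and correlation, even 0.2 to 0.4 EF points would raise false significance at n = 23 from 5% to between 37% and 90%. These are conditional rates, not a forecast that such drift will occur. Cancellation in the controlled contrast assumes the drift is the same on both days.

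The contrast also has a limit. NaHCO3 matches volume and time but not solute: Table 2 gives 0.12 M against 0.8 M, a ratio of 0.8/0.12 = 6.7, so a solute-load effect would remain.

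**What to change.** For Group II, name these as the main analyses:

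1. For EF first, then other MRI endpoints and 15O-water blood flow: the within-patient contrast of post − pre on the β-OH-B day minus post − pre on the NaHCO3 day.
2. For FDG uptake: the paired comparison of the β-OH-B and NaHCO3 sessions.

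Add a period term where session order is randomised. State the MRI order; if it is fixed, report that order is confounded with treatment. Label before-after results in Groups I and III as uncontrolled, and state the solute mismatch as a limitation.

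The cost is analysis wording, since the sessions are already scheduled. The downside is a larger standard error unless the two session changes correlate at 0.5 or more, so the sample-size section should restate power for this contrast. On its present inputs the loss is small against a 4.5-point target. If the SD of change were instead the hypothetical 6.36, power for that target at n = 23 would be 63%, 75% or 90% at r = 0, 0.25 or 0.5.

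Separately, the Group III rate gives (4.0 × 20 + 2.0 × 160)/100 = 4.0 mL/kg by 180 minutes, which reaches 300 mL at 300/4.0 = 75 kg. The passages on infusion rates and the volume limit must be reconciled.

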**Study Protocol:** Up to 100 Study participants will be asked to fast prior to consenting to the study and the day of the screening visit (day -30 to -7) participants will first sign consent form and eligibility criteria (A1c, eGFR, BP etc) will be confirmed and subjects will undergo a medical history and physical exam to exclude major organ system diseases other than diabetes and cardiac disease. Routine blood chemistries, CBC, urinalysis, lipid profile, TSH/T4, NT-proBNP, and EKG will be obtained. Blood pressure will be measured after reclining for 5 minutes in a quiet room and the mean of three measurements will be recorded. Subjects also will have a DEXA to measure total body fat content. If patient has not had an ECHO within 3-6 months of the screening visit, we will refer patient to the cardiac ECHO to confirm that the EF is < 50% (76).

Within 1-4 weeks after the screening visit, subjects will return to the Research Institute (RI) at 0700 h for a cardiac MRI (19,77) to confirm that the EF is < 50% and to obtain quantitative measures of baseline cardiac functional parameters: chamber volumes and pressures, wall thickness, LV diastolic function (E/A ratio, peak LV filling rate, diastolic volume) and LV systolic function (cardiac output, stroke volume, systolic volume, peak LV ejection rate). Strain and tagging also will be measured. To reduce the likelihood of hypoglycemia during the study procedures, subjects will be asked to withhold their antidiabetic therapy on the day of the studies until they have received a meal at the end of the study days.

Cardiac MRI will be performed by [name]. (Professor, Department of Radiology, UTHSCSA) on 3.0T MRI System (TIM, Trio, Siemens Medical Solution, Malvern, PA) with six channel anterior phased-array torso coil and corresponding coil elements (12 channels total) (19,77). Before cardiac MRI, catheters will be inserted into both antecubital veins for all blood withdrawal and  $\beta$ -OH-B infusion, respectively. Three blood samples will be drawn at 10-15 minute intervals for measurement of NT-proBNP, -OH-butyrate, acetoacetate,

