These 3 infusion rates were chosen to cover the range of observed increments in plasma ketone concentrations in type 2 diabetic patients treated with a SGLT2 inhibitor: a  $\beta$ -OH-B increment of ~0.5 mmol/L typically is seen in diabetic individuals treated with an SGLT2 inhibitor, while a  $\beta$ -OH-B increment of 2-5 mmol/L is observed in ~5-10% of individuals (54-62). After 5 (or 2) hours of  $\beta$ -OH-B infusion, the cardiac MRI will be repeated. All baseline blood samples will be repeated at 360, 365, and 370 minutes (6 hours) or at 180, 185, and 190 minutes (3 hours) after the start of the  $\beta$ -OH-B infusion. Based upon prior studies from our group (42), we expect to reach steady state levels of  $\beta$ -OH-B in 60 minutes; this will be documented by measuring  $\beta$ -OH-B (and acetoacetate) levels every 30-60 minutes throughout the study. From the study of Gormesen et al (70), we know that 6 hours is sufficient to see a significant reduction (by 50%) in myocardial glucose uptake in normal-glucose-tolerant subjects. Blood glucose and electrolytes are monitored throughout the study with the instantaneous-result device (iSTAT Handheld Analyzer), and potassium supplement may be given before the start of the  $\beta$ -OH-B infusion to prevent decrease in blood potassium level. The investigator will decide to give 20-40mEq of KCL to subjects with initial potassium in the low limit of normal. The investigator will make this decision based on the risk of the subject to develop low serum potassium based on their medical history and renal function. The contraindication for KCL supplementation is elevated blood potassium. It is unlikely that diabetic patients w not taking an insulin secretagogue (i.e. sulfonylureas) will develop hypoglycemia.

Therefore, individuals with history of taking insulin secretagogues (i.e. sulfonylureas) will have hourly glucose monitoring during the  $\beta$ -OH-B infusion to ensure early detection of hypoglycemia. If at any time a subject develops any symptoms suggestive of hypoglycemia (i.e. anxiety, diaphoresis, hunger, weakness etc.) glucose will be measured immediately. If hypoglycemia occurs, we will treat subjects with 15 grams of rapid acting carbohydrates (i.e. juice), and re-check subject's blood glucose level in 15 minutes, and repeat if necessary, until normoglycemia has been reached.

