### **Myocardial Glucose Uptake: F-2-deoxyglucose/PET**

The same 19 diabetic subjects who received the  $\beta$ -OH-B infusion designed to raise the plasma  $\beta$ -OH-B concentration by 2 mmol/L (Group II) will receive a cardiac positron emission tomography (PET) study to examine the effect of hyperketonemia on myocardial glucose uptake and blood flow. The PET study will be performed with subjects lying comfortably in the scanner as previously described (19,78,79). Subjects will report to the Research Imaging Institute at 0700 following a 10 hour overnight fast. PET scans will be performed in two-dimensional imaging mode using ECAT 931-08/12 PET scanner (CTI, Knoxville, TN) with 10.5-cm axial field of view and resolution of  $8.4 \times 8.3 \times 6.6$  mm^3 full width at half-maximum. Point-of-care urine pregnancy test will be done for women of reproductive age prior to injection of radioisotopes. A catheter (for arterialized blood withdrawal) is placed in a vein on the dorsum of the hand, which rests in a box heated to 60°C, and three baseline blood samples are drawn at 15 minute intervals. A second catheter for infusion of test substances is inserted into an antecubital vein. Following optimization of subject position, a 20-minute transmission scan will be performed after exposure of a retractable 68Ge ring source to correct emission data for tissue attenuation of gamma photons. Then, O-water (10.5 MBq/kg) is administered intravenously through the catheter over 20 seconds at infusion rate of 10 ml/min and PET scan is performed to measure myocardial blood flow (MBF), as previously described (19,78,79).

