At time zero a prime-continuous infusion of  $\beta$ -OH-B (prime = 1.5 mg/kg.min for 20 minutes; continuous infusion = 0.75 mg/kg.min) is started and continued for 380 minutes, and blood samples are drawn approximately every 30 to 60 minutes during the infusion. At 250 minutes to the start of the  $\beta$ -OH-B infusion, a 20-minute transmission scan is performed followed by a repeat cardiac O-water-PET study. At 300 minutes [F]fluoro-2-deoxy-D-glucose (185 MBq) is injected and a dynamic PET scan is performed for measurement of myocardial glucose uptake as previously described (19,78,79). At 360 minutes to the start of the  $\beta$ -OH-B infusion, two consecutive 20-minute dynamic scans of the abdominal and thigh area are performed to measure kidney and skeletal muscle glucose uptake. Urine will be collected before and after the 18F-FDG-PET scan to calculate endogenous glucose production (80). In ~14-30 days subjects will return for a repeat 18F-FDG-PET study with one exception: NaHCO3 will be infused instead of  $\beta$ -OH-B. The two studies will be performed in random order. All radioactive tracers are produced at the on-site cyclotron radiochemistry facility in the RadiolImaging Institute (RII) at the UTHSCSA.

For subjects in Group II, cardiac MRI studies (two study days, one with  $\beta$ -OH-B and other with NaHCO3 infusion) are performed before PET studies. Depending on the scanner availability, however, we may choose to perform PET studies before the cardiac MRI studies.

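### The only planned correlation uses myocardial β-OH-B uptake, which no procedure measures; glucose uptake is measured at one dose only, and the NaHCO3 control that aim (ii) depends on has no named analysis

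*Combined protocol and SAP*

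**What the plan says.** **Analysis.** The Statistical Analysis section names three things. A paired two-sided t-test "will be used to evaluate the null hypothesis of no difference between baseline and post" β-OH-B. A Pearson correlation of changes in "LV diastolic and systolic function and coronary blood versus changes in myocardial" β-OH-B uptake (a word, presumably flow, is missing after blood). ANOVA for EF changes across the three infusion groups. NaHCO3 is not mentioned.

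**Measurements.** On MRI days (Study Protocol), "catheters will be inserted into both antecubital veins for all blood withdrawal" and for the infusion. On PET days the sampling catheter "is placed in a vein on the dorsum of the hand", heated to arterialize the blood. 15O-water flow is scanned before and during the infusion. FDG is given once per PET day: at 300 minutes it "is injected and a dynamic PET scan is performed for measurement of myocardial glucose uptake as previously described".

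**Who has PET.** Only the Group II subjects (+2 mmol/L) "will receive a cardiac positron emission tomography (PET) study to examine the effect of hyperketonemia on myocardial glucose uptake and blood flow". They have one PET day with β-OH-B and one with NaHCO3, in random order. Table 1 (Groups I and III) lists no PET.

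**Aims.** The Specific Aim applies three increments to both LV function and myocardial glucose uptake. Rationale (7) says a dose response in myocardial glucose metabolism will be examined, and Expected Results anticipates a dose-dependent fall in glucose utilization.

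**The concern.** A planned analysis needs a data source for each variable, and each aim needs a contrast that the design supplies and the plan names. Here the only correlation lacks one of its two variables. Aim (ii) is worded across three doses but measured at one. The contrast that does answer it, β-OH-B day versus NaHCO3 day, is not in the analysis section. Left alone, the sponsor would have to choose a substitute correlate and the FDG test after seeing data, among many LV parameters. The MRI time control in Group II is in the same position: collected, but not assigned to any comparison.

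**Working it through.** **1. Is myocardial β-OH-B uptake obtainable?** It needs a labelled ketone or an arterial-to-coronary-venous difference. The PET section and Table 2 list 15O-water (flow) and 18F-FDG (glucose) only. Sampling is antecubital or from an arterialized hand vein. The Data Analysis section derives no ketone uptake. Magnetic resonance spectroscopy is named in Rationale (7), but for LV function and glucose metabolism, and it appears in neither schedule. Patients with the variable: 0.

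**2. Each measured quantity against the named paired test (baseline versus post β-OH-B).**

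| Quantity | Groups | Same-day baseline? | Named test applies? | NaHCO3 comparison named? |
|---|---|---|---|---|
| LV parameters (MRI) | I, II, III | yes | yes | no (control exists in II) |
| 15O-water flow | II | yes | yes | no |
| FDG glucose uptake | II | no | no | no |

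The gap is absolute for FDG. For LV parameters and flow the pre/post test runs but leaves the time control unused.

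**3. Doses with glucose uptake:** 1 of 3. One dose against control estimates one effect, not a dose-response.

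**4. What Group II can detect** (80% power, two-sided 0.05). The group has 19 subjects in the Study Protocol and PET sections, or 23 evaluable of 26 recruited in Sample Size.
- Correlation, Fisher approximation: r = tanh[(1.960 + 0.842)/√(n−3)] = tanh(2.802/4) = 0.605 for n=19, and tanh(2.802/√20) = 0.556 for n=23. Simulation (200,000 runs per value) shows these are slightly high, with power 0.82 at each. Power of 80% is reached at about r = 0.59 (n=19) and 0.545 (n=23).
- Paired FDG comparison (noncentral t): standardized difference 0.68 (n=19) or 0.61 (n=23).

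**5. MRI-to-PET separation.** Table 2 places the first PET at "Day 7-30 after MRI Study 2", with the same 7 to 30 day interval between the two MRI visits and between the two PET visits.
- PET in Table 2 order: each PET is (7+7) to (30+30) = 14 to 60 days after its matching MRI.
- PET order reversed, as randomization allows: NaHCO3 PET 7 to 30 days after its MRI; β-OH-B PET (7+7+7) to (30+30+30) = 21 to 90 days after its MRI.

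The PET text gives about 14 to 30 days between PET sessions, which raises the lower limits that involve the second PET by 7 days. It also allows PET before MRI.

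**6. If plasma β-OH-B change is the substitute.** Pooling Groups I and II (increments 0.5 and 2.0), the between-group variance is [(2.0 − 0.5)/2]² = 0.5625. The mean within-group variance is CV² × (0.5² + 2.0²)/2 = 2.125 CV². Between-group share = 0.5625/(0.5625 + 2.125 CV²):
- CV 14%: 0.93
- CV 30%: 0.75
- CV 50%: 0.51

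The CV range is my assumption; 14% is 0.5/3.5, from the healthy-subject study cited in Rationale (7). Group III does not belong in the same fit, because MRI is repeated "After 5 (or 2) hours of" infusion, with the shorter time applying to that group.

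**The case against.** The strongest reply is that uptake of β-OH-B is a slip for glucose uptake. FDG is the only myocardial substrate uptake measured, coronary flow comes from the same Group II sessions, and the group's earlier work, described in Rationale (1), related PET/FDG findings to LV function. That is plausible, and it is why the sponsor should be asked first. It does not rescue the text, which would still need the Group II restriction and a defined difference.

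A second reply is that plasma level can stand in for uptake, since Rationale (4) calls them proportional. The same sentence calls the process saturable, and the analysis section does not propose the substitution.

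Third, the missing FDG test is only a missing sentence, since the paired data exist. That stands: this part is an omission, not a design fault.

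A reader might go further and infer that an invalid glucose dose-response test is planned, or that a null LV result in Group III would be uninterpretable. Neither is supported. The analysis section plans no glucose dose-response test; the mismatch is between stated aim and design. Plasma β-OH-B is measured in Group III and gives indirect evidence of substrate exposure. Expected Results poses the null case as hypothetical and also offers longer infusion as an explanation. The wording there, and the spectroscopy reference, are minor.

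**Conclusion.** The point holds and should be corrected. The planned correlation cannot be run, because one variable is measured in no patient. Aim (ii) can be answered at +2.0 mmol/L versus NaHCO3 only. That contrast is unnamed for PET, and the NaHCO3 control is likewise unused for MRI.

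These conclusions come from tracing variables to procedures and need no numerical assumption. The detectable effects are context for the repair: they assume bivariate normality for r and 19 or 23 evaluable patients.

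The documents do not support reading this as a failure of the main EF analyses. The EF pre/post tests and the three-group EF ANOVA can still be run; in Group II the pre/post test should be accompanied by the NaHCO3-controlled comparison.

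**What to change.** 1. **Correlation.** Replace myocardial β-OH-B uptake with a measured variable; the sponsor states which was meant.
   - *If glucose uptake:* restrict to Group II and label it exploratory. For FDG use the β-OH-B-day minus NaHCO3-day value. For LV parameters and 15O-water flow use the within-day change on the β-OH-B day minus that on the NaHCO3 day. Note that MRI and PET fall on separate days, and state the detectable r (about 0.59 or 0.545).
   - *If plasma exposure:* use the mean of the three end-infusion samples minus the mean of the three baseline samples, labelled an exploratory exposure-response association. Analyse Group III apart and report the fit with a group term. State that any pooled fit over Groups I and II largely repeats the group contrast and may be confounded, since the Study Protocol describes no randomization to group.
2. **NaHCO3 control.** Name a paired β-OH-B versus NaHCO3 comparison in Group II for FDG uptake (day values) and for LV parameters and flow (within-day changes).
3. **Aim (ii).** Restate it, and the glucose expectation in Rationale (7) and Expected Results, as the effect of +2.0 mmol/L versus NaHCO3.
4. **Minor wording.** Correct the spectroscopy reference, and do not presume measured substrate uptake in Group III; keep the infusion-duration alternative.

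**Cost:** a protocol text amendment and analysis code, with no new procedures or visits. The glucose claim narrows to one dose. Plasma level is exposure, not uptake, and the group-term fit has little within-group spread to work with.
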